Title: Efficacy of the Autoimmune Protocol Diet for Inflammatory Bowel Disease

Date of Document: March 1, 2016 NCT number: (not yet assigned)

Study Protocol and Statistical Analysis Plan

Protocol ID: 16-6774

Sponsor: Scripps Health

Responsible Party: Principal Investigator, [name], MPH

Affiliation: Scripps Health

Study Start: September 1, 2016 (actual)

Primary Completion: December 10, 2016 (actual) Study Completion: December 10, 2016 (actual)

Title: Efficacy of the Autoimmune Protocol Diet for Inflammatory Bowel Disease PI: [name], MPH

1. SPECIFIC AIM: The aim of this study is to determine the potential efficacy of dietary therapy, the Autoimmune Protocol Diet (AIP Diet), in adult patients with active Crohn's disease (CD) or ulcerative colitis (UC).

2. RESEARCH DESIGN/METHODS:

- **A.** Primary Outcome Measure: Change in clinical disease activity for CD and UC from baseline to 11 weeks (study completion)
- For CD, clinical activity will be defined by the Harvey Bradshaw Index (HBI). Clinical remission is defined as a HBI<5, Clinical response is defined as a reduction in the HBI of at least 3 points.
- For UC, the Mayo Clinic Score (MCS) will be used to assess disease activity. Clinical remission is defined as a MCS of ≤2 and no subscore >1. Clinical response is defined as a reduction in the MCS of at least 3 points and a decrease of 30% from the baseline score, with a decrease of at least 1 point on the rectal bleeding subscale or an absolute rectal bleeding score of 0 or 1.
- **B.** Secondary Outcome Measures:
- For CD, changes in endoscopic activity will be defined by the Simple Endoscopic Score in Crohn's Disease (SES-CD) from most recent endoscopic evaluation prior to starting treatment with the AIP diet to 11 weeks (study completion). We will assess (a) Endoscopic remission, defined as an SES-CD of 0-2, and (b) Endoscopic response, defined as a decrease of 50% from the baseline SES-CD
- For patients with small intestinal CD not amenable to endoscopic evaluation, changes in inflammatory activity will be assessed by radiographic changes as measured by CT or MR enterography or video capsule endoscopy at baseline and 11 weeks (study completion).
- For patients with UC, changes in endoscopic activity will be defined by the Mayo Clinic endoscopic subscore that comprises the MCS: We will assess (a) Endoscopic remission, defined as a Mayo endoscopic subscore of 0 or 1, and (b) Endoscopic response, defined as improvement in the Mayo endoscopic subscore by 1 point.
- Change in common laboratory measures, histologic activity, micronutrient levels (vitamin D, iron studies), use of steroids, and any adverse events resulting in flare or hospitalization from baseline to 11 weeks
- Where possible, assess changes in RNA expression from intestinal mucosal biopsy specimens from baseline to 11 weeks
- Assess changes in fecal microbial populations from baseline to 11 weeks, and compare with fecal microbial populations from IBD controls in clinical and endoscopic remission
- C. Study Design: Twenty participants with CD or UC with mild or moderate disease activity, as defined by HBI ≥ 5 for CD or Partial Mayo Clinic Score ≥ 3 for UC, ages 18 and over will enroll into this study for treatment with the AIP diet. Each patient will receive an initial evaluation including a physical exam, medication review, nutritional guidance and post treatment evaluations. We will also identify 10 patients with CD or UC in clinical and endoscopic remission and obtain a single stool sample for fecal calprotectin (inflammatory marker in stool) and microbiome analysis as our positive controls.
- Inclusion Criteria (Participants):
 - 1. At least 18 years of age

- 2. Able to provide written informed consent prior to screening and to comply with the requirements of the study protocol.
- 3. Established diagnosis of small bowel CD or colonic CD or ulcerative colitis
- 4. Confirmation of active CD or UC with recent (within 3 months) objective evidence of endoscopically active disease on colonoscopy or CT/MR enterography or video capsule endoscopy
- 5. Any medications being currently used for IBD must remain stable during the study period with the exception of tapering of corticosteroids.
- 6. Current disease activity defined as a Harvey Bradshaw index ≥ 5 at baseline for CD or Partial Mayo Score ≥ 3 for UC
- 7. Established Facebook account
- 8. Comfortable with internet-based surveys and email

- Exclusion Criteria (Participants):

- 1. If female, is pregnant or is breast feeding
- 2. Known celiac disease or subjects with a positive screen for celiac disease (elevated tissue transglutaminase antibodies)
- 3. Inability to provide informed consent or unwilling to participate
- 4. Evidence of untreated infection (e.g. Clostridium difficile)
- 5. Presence of stoma or J pouch
- 6. Bowel surgery within 12 weeks prior to enrollment and/or has surgery planned or deemed likely for IBD during the study period
- 7. Use of oral or intravenous antibiotics within 4 weeks prior to study initiation
- 8. Use of tube or enteral feeding, elemental diet, or parenteral alimentation within 4 weeks prior to study initiation
- Study Process: (Note: SOC indicates standard of care)
 - Enrollment: Enrollment will take place over 2 months prior to study initiation. Participants will be screened by SCMG gastroenterologists, and informed consent will be obtained by the study coordinator (SC). At enrollment, the SC will document relevant history and physical examination, current prescription and nonprescription medications, and any imaging, endoscopic, and histologic evaluation completed for IBD. Participants will undergo SOC stool testing for common infections (unless completed within 3 months) and one 5mL blood draw into PAX tube for future genotyping.
 - 1 week prior to study initiation: Participants will undergo SOC testing for CBC, HFP, vitamin D, iron studies, CRP, and fecal calprotectin. They will also establish online membership in the "SAD (Standard American Diet)-to-AIP (Autoimmune Paleo) Diet Transition Program" run by [name], and receive two books on AIP diet and recipes ("The Paleo Approach: Reverse Autoimmune Disease and Heal Your Body" by Ballantyne and "The Autoimmune Paleo Cookbook: An Allergen-Free Approach to Managing Chronic Illness" by Trescott).
 - Study initiation/Treatment with AIP diet: Intervention will be based on a 6-week transition to the AIP diet and 6-week maintenance phase on the AIP diet (no food group reintroduction allowed), using the "SAD-to-AIP Diet Transition Program." Patients will receive certified health coaching and one-on-one and group guidance by a registered dietician, along with group-based coaching through a private and secret Facebook group. During the study, participants will record daily dietary intake, which

will be reviewed by program team. They will also complete surveys regarding feasibility, tolerability, and adherence to AIP diet every 3 weeks during the study.

- Use of medications/supplements during study: Any medications, vitamins or supplements that participants are taking for at least 1 month prior to study initiation may be continued during the study period. During the 12 week study, however, participants will not be allowed to add, remove, or change doses any medications, vitamins or supplements, unless there are concerns related to IBD activity or flare, side effects or potential toxicity. The only exception to medication change is that steroid tapering will be allowed during the 12 week period. Any unanticipated changes to a patient's medication regimen will be recorded.
- Physician follow-up during study: Each participant will have clinical follow-up with their SCMG gastroenterologist during the week prior to enrollment, at 6 weeks, and at 11 weeks. Routine history and physical examination, as well as medication assessment, will be performed at these visits. In addition patients will undergo SOC blood work for CBC, HFP, vitamin D, iron studies, and CRP at 12 weeks. Fecal calprotectin will be performed at weeks 6 and 11.
- Intestinal biopsy and RNA sequencing: RNA-sequencing is a widely used next-generation sequencing technology which is used to study the expression patterns of genes in intestinal samples. A typical RNA-seq analysis pipeline involves demultiplexing of samples and quality control checks followed by alignment to a reference genome and finally counting the sequences aligned to various genes. The counts are then used to quantify expression levels of genes or compare samples using differential expression analysis. Where possible, patients undergoing endoscopic assessment at baseline will have 2 intestinal biopsy specimens collected in RNAlater for RNA sequencing. All patients will undergo standard of care endoscopic or radiographic reassessment of IBD activity at 11 weeks (study completion), with 2 intestinal biopsy specimens collected in RNAlater.
- Microbiome Analysis: 16S ribosomal RNA sequencing is a commonly used method to identify and quantify microbial species in a microbiome sample. Sequencing can be performed using an Illumina MiSeq machine which outputs anywhere from 10-20 Million paired-end 300 bp reads. Analysis will be performed using "mothur," an open-source software, with subsequent pipeline steps obtained to estimate species diversity and subtypes. Stool assessment for microbiome analysis from participants will be performed during the week prior to study initiation, and weeks 2, 4, 6, and 11. Stool assessment from positive controls will be performed during enrollment or the study period.

D. Statistical Analysis:

Analyses for the primary outcome will be conducted for participants with CD or UC and for the entire cohort. Paired t test will be used to examine differences between baseline and week 6 or 11 outcomes among those with follow-up data at those time points. Fisher's exact test will be used to examine whether IBD type is associated with the primary outcome. Survey data will be analyzed using descriptive statistics, including frequencies, percentages, means, and modes, as well as ANOVA. Relationships between bivariate categorical variables, including diet adherence and IBD type, will be tested using Chi-Square or Fisher's Exact Test, as appropriate.

RNA analyses: To identify genes which are differentially expressed due to the dietary intervention, we will first control for patient level differences using a Bayesian hierarchical mixture model, which estimates the log fold change for each gene and calculates a probability of the gene being differentially expressed (P(DE)). Significant genes will be selected considering a 5% Type 1 error rate i.e. P(DE)>0.95. Gene Ontology enrichment will be done for significantly up-regulated and down-regulated gene using DAVID. DAVID is a web-based application that ranks biologically relevant gene sets enriched in the gene list being interrogated using a modified Fisher Exact test.

Microbiome analyses: 16S ribosomal RNA sequencing is a commonly used method to identify and quantify microbial species in a microbiome sample. Sequencing will be performed using an Illumina MiSeq machine which outputs anywhere from 10-20 Million paired-end 300 bp reads. Analysis will be performed using "mothur," an open-source software, with subsequent pipeline steps obtained to estimate species diversity and subtypes. Stool assessment for microbiome analysis from participants will be performed using mail-in FTA cards during the week prior to study initiation, and weeks 2, 4, 6, and 11.

We will also identify at least 10 patients with CD or UC in clinical, endoscopic, and histologic remission and obtain a single stool sample using mail-in FTA cards for microbiome analysis as our positive controls. Stool assessment from positive controls will be performed during study enrollment or the study period to avoid any temporal bias. In this way we will be able to characterize whether, within 11 weeks of the AIP diet, the microbiome profile changes over time due to dietary intervention are on a trajectory towards normalization based on changes in the degree of similarity with profiles from IBD patients already in remission. Diversity within individual samples and similarity between individuals and time-points will be measured using diversity metrics commonly used in ecological studies. These summary metrics will be utilized to determine whether clinical response can be correlated to microbiome normalization or other diversity changes.

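### Endoscopic remission carries no baseline condition and entry sets no endoscopic minimum, so a patient who starts in the remission range would count as a remission without any change

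*Combined protocol and SAP*

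**What the plan says.** All references are to the combined protocol and SAP.

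- **Section 2.B, UC.** Two endoscopic outcomes are listed side by side: "Endoscopic remission, defined as a Mayo endoscopic subscore of 0 or 1" and "Endoscopic response, defined as improvement in the Mayo endoscopic subscore by 1 point". The second is a change from baseline; the first is not.
- **Section 2.B, CD.** The parallel pair is "Endoscopic remission, defined as an SES-CD of 0-2" and "Endoscopic response, defined as a decrease of 50% from the baseline SES-CD". The baseline SES-CD comes from the last endoscopy before the diet starts, with no time limit. Small-bowel CD that cannot be reached by endoscopy has a separate imaging or capsule outcome.
- **Section 2.C, Inclusion Criteria.** Item 4 requires, within the previous 3 months, "objective evidence of endoscopically active disease on colonoscopy or CT/MR enterography or video capsule endoscopy". Item 6 sets the numeric entry limits: HBI of at least 5 for CD and "Partial Mayo Score ≥ 3 for UC". Neither item gives an endoscopic score.
- **Section 2.D, Statistical Analysis.** Baseline is compared with week 6 or week 11 by paired t test in those with follow-up data. No denominator is given for endoscopic remission, and no patient is left out for already meeting the definition at baseline.

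**The concern.** A remission rate is normally read as the share of patients whose active disease resolved. That reading is safe only if nobody starts in the remission range. The plan secures this for clinical remission in CD: entry at HBI of 5 or more is the exact complement of remission at HBI below 5. It has no matching arrangement for endoscopic remission. The term for active disease in criterion 4 is not tied to a score, and the examination that qualifies a patient need not be the one that supplies the baseline score.

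The study has no control arm, so no comparison group would show how much of a remission rate reflects healing and how much reflects patients who never exceeded the threshold. With 20 participants split over two diseases, a few such patients could shift a reported rate noticeably.

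**Working it through.** The plan states no expected endoscopic remission rate, so there is no figure to reproduce. The check has four steps.

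**1. Which courses count as UC remission?** Assume the Mayo endoscopic subscore runs from 0 to 3, which gives 4 × 4 = 16 pairs of baseline and week-11 scores.

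| Baseline → week 11 | Remission (0 or 1) | Response (1-point improvement) |
|---|---|---|
| 1→0, 2→0, 2→1, 3→0, 3→1 | yes | yes |
| 0→0, 1→1 | yes | no (unchanged) |
| 0→1 | yes | no (worse) |
| 3→2 | no | yes |
| the other 7 | no | no |

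Eight pairs end in remission, and three of the eight show no improvement. A baseline of 0 is hard to reconcile with criterion 4, so the realistic UC case is 1→1. Every remission from baseline 2 or 3 is also a response.

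**2. Can such a patient be enrolled?**
- *CD.* Criterion 4 can be met on enterography or capsule alone. The separate imaging outcome covers only small-bowel disease that cannot be scoped. A patient who qualifies on imaging and can be scoped stays in the SES-CD analysis, and nothing requires that patient's baseline SES-CD to exceed 2.
- *UC.* A patient at subscore 1 is eligible if the clinician judges that score to be active. The documents neither say so nor exclude it.

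**3. Effect on the reported rate.** Let f be the share in range at baseline, s the share of those in range at week 11, and r the remission rate among the rest. Then

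reported rate = f·s + (1−f)·r, and reported rate − r = f·(s − r).

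All values of f, s and r are assumptions.

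| f | s | r | Calculation | Reported |
|---|---|---|---|---|
| 0 | any | 20% | 0 + 1 × 0.20 | 20% |
| 10% | 100% | 20% | 0.10 + 0.90 × 0.20 | 28% |
| 20% | 100% | 20% | 0.20 + 0.80 × 0.20 | 36% |
| 30% | 100% | 20% | 0.30 + 0.70 × 0.20 | 44% |
| 20% | 0% | 20% | 0 + 0.80 × 0.20 | 16% |

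The rate is overstated when s > r, understated when s < r, and undistorted when f = 0. If no patient's status changes (s = 100%, r = 0), the reported rate equals f. In a disease group of 10 (assumed), one patient in range at baseline is f = 10%.

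**4. SES-CD response at low baselines.** The percentage decrease is (baseline − week 11) / baseline. At baseline 0 this divides by zero. If the rule were programmed as week 11 ≤ 0.5 × baseline, 0→0 would pass as a response. At baseline 2, a fall of a single point meets the 50% rule.

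**The case against.** The strongest reply is that criterion 4 already closes the gap. It demands endoscopically active disease, the plan calls subscore 0–1 and SES-CD 0–2 remission, and section 2.C sets the participants against 10 controls in remission. Read naturally, active disease and remission do not overlap, so f = 0. This has real force. It closes most of the UC route, and it is why the effect can only be stated conditionally. It does not close the CD route, because a patient can be active on imaging or capsule under any reading and still have a baseline SES-CD of 0–2. The non-overlap itself is also not written down.

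A second reply is that both definitions sit under changes in endoscopic activity and are paired with a response outcome, so a before-and-after display would expose patients who started in range. The response outcome indeed does not count an unchanged UC patient. But remission is listed as an outcome of its own, and no such display is specified.

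Third, this is a secondary outcome with no test or success threshold attached, in an uncontrolled study of 20. That limits the weight of the point but leaves the ambiguity in place.

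A reader might also infer that admitting "Twenty participants with CD or UC with mild or moderate disease activity" implies low endoscopic scores. It does not: the plan ties that severity to HBI and Partial Mayo, not to endoscopy.

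**Conclusion.** The point holds in conditional form. Remission is a week-11 state with no baseline condition, and entry sets no endoscopic minimum. A scopeable CD patient who qualifies on imaging, or a UC patient judged active at subscore 1, could therefore be enrolled and would be counted as a remission without change. The SES-CD response rule is undefined at baseline 0.

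The distortion is f·(s − r). With assumed r = 20% and s = 100%, that is 0 points at f = 0, 16 points at f = 20% (36% against 20%) and 24 points at f = 30% (44% against 20%). The documents give no value for f, s or r, and f may be zero.

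Three stronger readings are not supported:
- That unchanged patients *are* counted as remissions. This depends on who enrols and on how an undefined term is applied.
- That the bias always favours the diet. It does so only when s > r; with f = 20%, r = 20% and s = 0 the reported rate is 16%.
- That endoscopic remission is the study's most objective result. The documents do not rank it so, and CRP and fecal calprotectin are also collected.

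The issue should be corrected because the remedy is cheap. It concerns a secondary outcome and does not touch the primary analysis.

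**What to change.** Change the analysis wording in section 2.B only; eligibility stays as it is.

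1. Report endoscopic remission among patients who do not meet the definition at baseline: Mayo endoscopic subscore of 2 or more for UC, SES-CD of 3 or more for CD.
2. Report SES-CD response among patients with a baseline SES-CD of 3 or more.
3. State how many patients are excluded from each denominator for this reason.
4. Show a baseline-by-week-11 shift table of endoscopic scores for all patients, including those excluded.

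With step 1, unchanged courses such as 2→2 and 3→3 do not meet the definition, so no unchanged patient can be a remission. If nobody starts in range, the exclusion counts are zero and the rate is unaffected.

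No new procedure is needed: prior endoscopy is documented at enrollment and reassessment is planned at 11 weeks. The cost is smaller denominators in already small disease groups, and possibly a less favourable remission rate.

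### No dose-stability window before the diet: a recent increase in a long-used IBD drug meets the written rules, and any effect appearing after baseline counts as change on the diet

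*Combined protocol and SAP*

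**What the plan says.** Section 2.C, Inclusion Criteria (Participants), item 5: "Any medications being currently used for IBD must remain stable during the study period with the exception of tapering of corticosteroids".

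Section 2.C, Study Process, Use of medications/supplements during study, has two rules. Drugs and supplements "that participants are taking for at least 1 month prior to study initiation may be continued during the study period". Then: "During the 12 week study, however, participants will not be allowed to add, remove, or change doses any medications, vitamins or supplements". That sentence goes on to allow changes prompted by IBD activity or flare, side effects or possible toxicity. Steroid tapering is allowed, and unanticipated changes are recorded.

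On timing, the Enrollment paragraph says: "Enrollment will take place over 2 months prior to study initiation". The coordinator then documents "current prescription and nonprescription medications". Clinical visits are scheduled "during the week prior to enrollment, at 6 weeks, and at 11 weeks". The Study Design paragraph also mentions an initial medication review, without a date.

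Section 2.D gives the analysis: "Paired t test will be used to examine differences between baseline and week 6 or 11 outcomes". There is one treated group of 20. The remission controls give a single stool sample and no clinical comparison.

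**The concern.** Patients must have active disease to enter (inclusion items 4 and 6), and patients with active disease are those whose treatment is likely to have been stepped up. The documents do not say how often this happens. If a drug was increased a few weeks before the diet and is still taking effect, part of the improvement seen at week 6 or 11 belongs to the drug. With no control arm and no adjustment for medication, the paired test cannot separate that part from the diet's effect. Eligibility is one of the few places where this design can limit the problem.

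**Working it through.** **The rules side by side**

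| Rule | When it applies | Does it cover dose before initiation? |
|---|---|---|
| Inclusion 5 | study period | No |
| Ban on changes (Use of medications) | the 12-week study, with the flare/toxicity exception | No |
| 1-month look-back (Use of medications) | before initiation | No: duration of use only |
| Exclusions 6, 7, 8 | 12 weeks before enrollment (bowel surgery); 4 weeks before initiation (antibiotics; enteral or parenteral feeding) | No: other exposures |

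Take a patient on a drug for a year whose dose was raised two weeks before initiation. The drug has been taken for more than 1 month, nothing changes during the 12 weeks, and no exclusion applies. The patient qualifies.

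None of the planned medication checks asks for the date of the last dose change. The step one week before initiation lists laboratory tests and program set-up, with no medication recheck.

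**Size**

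The plan gives no SD, effect size, power or significance level for the primary outcome, so it has no figure to reproduce. Everything below is illustrative.

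Inputs:
- n = 20 (Study Design).
- Gain of 3 points: the drop used in both response definitions (section 2.A), taken here as the drug effect.
- Assumed: k = 1, 2 or 4 affected patients; probability p = 0.3-0.5 that an affected patient gains 3 points after baseline; normally distributed change with SD 3-4; no diet effect; two-sided 5% paired t test.

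*Shift in mean change* = 3 × k × p / 20:
- k = 1: 3 × 1 × 0.3 / 20 = 0.045 to 3 × 1 × 0.5 / 20 = 0.075
- k = 2: 0.09 to 0.15
- k = 4: 0.18 to 0.30

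*Chance of a significant improvement*, by simulation (400,000 trials per cell, no background improvement):

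| k | p = 0.3-0.5, SD 3 | p = 0.3-0.5, SD 4 | p = 1 (upper bound), SD 4 to SD 3 |
|---|---|---|---|
| 0 | 2.5% | 2.5% | – |
| 1 | 2.8-3.1% | 2.8-3.0% | 3.4-3.6% |
| 2 | 3.2-3.8% | 3.1-3.5% | 4.6-5.3% |
| 4 | 4.2-5.6% | 3.7-4.7% | 8.0-10.4% |

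An independent rerun with 200,000 trials per cell agreed within simulation error.

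*With background improvement.* Suppose a share r = 0.2-0.4 of all patients would gain 3 points anyway, and that drug and background gains do not add. The chance of a significant improvement is then already 9-33% with nobody affected. Affected patients add 0.5-2.0 (k = 1), 1.0-3.9 (k = 2) or 2.5-8.5 (k = 4) percentage points.

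*Response rate* (a drop of at least 3 points). In the normal model a patient with no shift already reaches 3 points with probability Φ(−3/SD): 0.159 at SD 3 and 0.227 at SD 4. A 3-point shift raises this to 0.50. Each shifted patient therefore adds 0.341 (SD 3) or 0.273 (SD 4) of a responder.

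Inflation = k × p × (1 − r) × (0.50 − Φ(−3/SD)) / 20:
- k = 1: 0.3 × 0.6 × 0.273 / 20 = 0.2 to 0.5 × 0.8 × 0.341 / 20 = 0.7 percentage points
- k = 2: 0.5 to 1.4 percentage points
- k = 4: 1.0 to 2.7 percentage points

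**The case against.** The strongest reply is that the text can be read more generously. To ask that a drug in current use remain stable presupposes that it is stable at screening, where gastroenterologists judge eligibility. The term study period is not defined. The evidence that it excludes enrollment is indirect: a sentence on control stool samples, "Stool assessment from positive controls will be performed during enrollment or the study period", treats the two as alternatives. For patients enrolled late, the medication list falls close to initiation. All of this is fair, but even if the study period included enrollment, a dose raised just before enrollment would still pass.

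A second reply is that the bias is small beside the missing control arm, and that the aim is only potential efficacy. That stands, and it limits the severity.

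Three stronger readings are tempting, and the documents do not support them:

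- *The drug's whole effect is credited to the diet.* Only the part that appears after baseline is. Benefit already realised is in the baseline score, and patients must still have HBI of at least 5 or partial Mayo of at least 3. For a recently raised steroid, the permitted taper may work in the other direction.
- *Every 3-point gain is a whole extra responder.* That would give k × p × (1 − r) / 20, or up to 8.0 percentage points for k = 4. It ignores patients who would cross the threshold anyway and those who still fall short after the shift, and is about three times too high under the normal model. For UC, response also needs a 30% fall and a rectal-bleeding condition, which would lower the figure further.
- *Dose changes on study are barred outright.* They are not, because of the flare and toxicity exception. Section 2.D does not say how such changes are handled. That is a separate and more direct source of confounding.

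**Conclusion.** The gap is real on the text: no rule requires a stable IBD drug dose before the diet starts. Its effect is probably modest. With 1 to 4 of 20 patients affected and no diet or background effect, the false-improvement rate moves from 2.5% to about 2.8-5.6%. With 20-40% background improvement, whole-cohort response is inflated by about 0.2 to 2.7 percentage points. These figures rest on assumed counts, response probabilities and SDs, none of which the documents give. The lack of a control arm matters more. This is a minor point, worth acting on because the change is cheap.

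**What to change.** Extend inclusion 5 along these lines: *each IBD medication must have been at an unchanged dose (corticosteroid taper excepted) for at least 1 month before study initiation, in addition to the existing requirement during the study.* Record the last dose-change date of each IBD drug at enrollment, and recheck it at the contact already planned one week before initiation, so that a change made after enrollment is caught.

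The cost is one line of eligibility wording, one date field and one recheck. A few patients may be delayed or become ineligible. One month may be too short for slow-acting drugs, so the bias is reduced, not removed. The change does not deal with dose changes made on study under the flare and toxicity exception.

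### Crohn's disease patients are selected on the HBI score from which change may be measured, so part of any improvement in this single-arm study may be regression to the mean; a separate pre-diet score would reduce it

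*Combined protocol and SAP*

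**What the plan says.** Section 2.C, inclusion criterion 6, sets the entry threshold: "Harvey Bradshaw index ≥ 5 at baseline for CD or Partial Mayo Score ≥ 3 for UC". Section 2.A defines the primary outcome as "Change in clinical disease activity for CD and UC from baseline to 11 weeks", with CD remission set at HBI below 5. Section 2.D compares baseline with week 6 or week 11 by paired t test. Twenty patients are treated in a single arm. The 10 patients in remission who serve as controls give one stool sample each and no repeated clinical score.

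No section dates the baseline HBI or Mayo score. Under Physician follow-up, patients have "clinical follow-up with their SCMG gastroenterologist during the week prior to enrollment, at 6 weeks, and at 11 weeks", and "Routine history and physical examination, as well as medication assessment, will be performed at these visits"; neither score is named. Enrollment runs over the 2 months before the diet starts. The week before initiation lists laboratory tests and calprotectin. By contrast, section 2.B does date the CD endoscopic baseline, taking change "from most recent endoscopic evaluation prior to starting treatment with the AIP diet to 11 weeks".

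**The concern.** In CD the same word, baseline, labels both the score that decides entry and the score from which change is measured. Patients admitted because a fluctuating score was high tend to score lower next time without treatment. With one treated arm, no second pre-diet score, no run-in and no adjustment, the paired test attributes that fall to the diet period.

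Remission is also the exact complement of the entry rule: a patient admitted at HBI 5 meets it with a 1-point fall. In a study of 20 patients meant to show potential efficacy, a spurious shift of a fraction of a point can influence the conclusion.

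UC is less direct. Entry uses the Partial Mayo score and the outcome is the full Mayo score. The partial score is presumably a component of the full one, and criterion 4 ("objective evidence of endoscopically active disease on colonoscopy or CT/MR enterography or video capsule endoscopy") can select on the endoscopic component as well.

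**Working it through.** The plan gives no power calculation, HBI mean, SD or between-visit correlation, so there is no figure of its own to reproduce. **Every distributional input below is assumed.**

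**Step 1: expected fall with no diet effect.** For integer HBI with entry at 5 or more, let a = (4.5 − mean)/SD. With independent visit-to-visit noise around a stable level,

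fall = SD × (1 − correlation) × φ(a) / (1 − Φ(a)).

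- SD 3.5, mean 5, correlation 0.6: a = −0.143, ratio = 0.395/0.557 = 0.709, fall = 3.5 × 0.4 × 0.709 = 0.99.
- SD 2, mean 8, correlation 0.9: a = −1.75, ratio = 0.0863/0.960 = 0.090, fall = 2 × 0.1 × 0.090 = 0.02.

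**Step 2: effect on the test.** Simulation with HBI rounded and floored at 0, correlation 0.6 to 0.9, 10 CD patients (the CD/UC split is not stated), two-sided 5% paired t test, and the qualifying score used as baseline:

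| Assumed screened patients | Mean fall (points) | Rejection |
|---|---|---|
| SD 3.5, mean 5 to 7 | 0.15 to 0.99 | 6 to 16% |
| SD 3.5, mean 7 to 8 | 0.11 to 0.58 | 5 to 9% |
| SD 2, mean 7 to 8 | 0.02 to 0.17 | about 5% |

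In the first row, 7 to 26% are below HBI 5 at week 11 with no diet effect; in the second, 5 to 15%. A mean of 5 implies that 44% of those screened score below 5. That sits poorly with criterion 4, so the lower rows are more plausible.

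**Step 3: effect of a separate pre-diet score (SD 3.5, mean 5 to 7).** With independent noise, the fall from the re-score to week 11 is 0.00 and rejection is 5%. The same 7 to 26% are below HBI 5 at the re-score and at week 11, a net gain of 0. If scores instead drift slowly (AR(1), correlation 0.6 to 0.9 over the 12 weeks from re-score to week 11):

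| Weeks between the two scores | Fall from qualifying score | Fall from re-score | Removed | Net rise in share below HBI 5, re-score to week 11 |
|---|---|---|---|---|
| 1 | 0.16 to 1.05 | 0.14 to 0.93 | 11 to 14% | 5 to 19 points |
| 4 | 0.20 to 1.21 | 0.14 to 0.81 | 30 to 34% | 4 to 13 points |
| 8.7 | 0.25 to 1.43 | 0.13 to 0.65 | 46 to 55% | 3 to 9 points |

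At 8.7 weeks, rejection is 6 to 23% from the qualifying score and 6 to 10% from the re-score.

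**Step 4: how early the qualifying score could be.** Read literally, the visit in the week before enrollment could precede the diet by up to 61/7 + 1 = 9.7 weeks. If the cover's study start (1 September 2016) means first enrollment, the 100 days to 10 December are 14.3 weeks. The gap is then at most 14.3 − 11 + 1 = 4.3 weeks, or 14.3 − 12 + 1 = 3.3 weeks if the 12-week duration is used.

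**The case against.** A reader might infer that the undated baseline produces the bias. It does not: selecting on the baseline score does, and adding a date alone would remove nothing.

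A reader might also infer that the qualifying score is taken many weeks before the diet and that no later visit exists. The documents do not settle this. The visit in question stands beside visits at 6 and 11 weeks, which naturally count from diet start, and laboratory tests and stool sampling are placed in the week before initiation. *Enrollment* may therefore be a slip for *study initiation*. In favour of the literal reading, the exclusions use the two anchors separately: "Bowel surgery within 12 weeks prior to enrollment" and "Use of oral or intravenous antibiotics within 4 weeks prior to study initiation". If initiation is meant, and eligibility was decided earlier at gastroenterologist screening, a later pre-diet visit already exists and the point shrinks largely to wording.

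Three further objections stand:

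- The bias may be negligible, as the SD 2 row shows, and even 0.58 points is small against the 3-point response threshold.
- A re-score only a week later achieves little if scores drift. Under independent noise, however, any gap removes the bias, so it would be wrong to say in general that a one-week gap helps little.
- Not re-applying the cut-off brings some patients with baseline HBI below 5 into a study of active disease. That is a real cost.

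None of these removes the selection on the baseline score, and nothing in the plan offsets it.

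**Conclusion.** The point holds conditionally: if the qualifying HBI is also the baseline, regression to the mean is counted as improvement. The direction is certain whenever the between-visit correlation is below 1. The size is not known.

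Under independent noise, 10 CD patients and correlation 0.6 to 0.9, the range is from about 0.02 points with rejection near 5% (SD 2, mean 8) to about 1.0 point with 16% (SD 3.5, mean 5). Slow drift over an 8.7-week gap raises the top to about 1.4 points and 23%. Criterion 4 favours the low end.

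The figures do not show that an observed improvement would be an artefact, or that the test's true error rate is 16% or 23%; those are the ends of an assumed range. No UC figure can be given, because the documents give no Mayo distribution, but this does not mean that UC is free of the problem. The change is worth making because it is cheap. Its benefit runs from about a tenth of the bias (drift, scores one week apart) to all of it (independent noise).

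**What to change.** 1. Reconcile the Physician follow-up text with the Study Process text: state whether the first visit is timed from enrollment or from study initiation.
2. Use the screening or enrollment score for eligibility only, and reword criterion 6 from *at baseline* to *at enrollment*.
3. Score HBI or Partial Mayo again in the week before the diet starts. The scheduled visit can supply this if it is timed from study initiation and eligibility was decided beforehand. Define this score as baseline in 2.A and 2.D, do not re-apply the cut-off, and keep all patients in the change analysis. Restricting to those still at HBI 5 or more would select on the new baseline again.
4. Report how many CD patients are already below HBI 5 at the re-score, next to week-11 remission in all CD patients. Record the days between the two scores. For UC, give the date of the endoscopic subscore, note that it may still carry selection, and report the Partial Mayo change beside the full Mayo change.
5. State that the re-score removes all of the bias under independent noise but only part under drift (about 11 to 14% at 1 week and 46 to 55% at 8.7 weeks in the assumed model), and that single-arm change cannot be attributed to the diet alone.

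The cover gives actual completion dates. If no further score can be taken, the report can still say which score served as baseline, give the days from that score to diet start, and carry the attribution statement.

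Cost: one short score per patient (20 in all) in a week that already has laboratory tests, possibly one added contact, and wording changes in criterion 6, 2.A, 2.C and 2.D. Some patients will have a baseline HBI below 5 in the change analysis, and the observed improvement will probably be smaller.
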